**Table 2. Clinical Laboratory Tests**

Hematology	Clinical Chemistry a	Urinalysis	Other Laboratory Tests
Hematocrit	BUN	Specific gravity	Serum pregnancy (bHCG) test c
Hemoglobin	Creatinine	Ketones	FSH d
RBC count	Total bilirubin	pH	HBs Ag
WBC count	ALT	Protein	HBs Ab
Neutrophils	AST	Blood	HBc Ab
Bands	Alkaline phosphatase	Glucose	HBV DNA PCR (reflex only)
Lymphocytes	CPK	Urobilinogen	HCV Ab
Monocytes	Sodium	Bilirubin	HCV RNA (reflex only)
Basophils	Potassium	Leukocytes	HIV Ab
Eosinophils	Chloride	Nitrites	QuantiFERON-TB Gold e
Reticulocyte count	Bicarbonate	Microscopic examination, if needed	hs-CRP
Platelet count	Calcium		International Normalized Ratio (INR) (reflex only) f
	Inorganic phosphate	Stool Samples	Lymphocyte Subsets g
	Uric acid	C. difficile toxin	PK
	Cholesterol	Fecal calprotectin	Beta-D-glucan test (Japan only)
	LDL-C		Local Lab Test:
	HDL-C		Urine pregnancy test h
	Triglycerides		
	Total protein		
	Albumin		
	Glucose		
	eGFR b		
Additional Samples Collected (Optional)			
Blood, serum, plasma, stool, and intestinal tissue samples for exploratory research, a biologic drug level. i			

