**Appendix C. Study Activities**

Activity	Part 1 – 12-Week Double-Blind Induction Part 2 – Open-Label Single-Arm Induction						Part 3 – Extended Treatment Period			Premature Discontinuation Visit	Unscheduled Visit b	30-Day Follow-Up Visit
	Screening a	Baseline	Week 2	Week 4	Week 8	Week 12	Week 16	Week 20	Week 24			
Informed Consent	X											
Inclusion/Exclusion c	X	X										
Medical/Surgical History c	X	X										
Prior and Concomitant Medications c,#	X	X	X	X	X	X	X	X	X	X	X	X
Physical Exam d,+ and Vital Signs e,#	X	X	X	X	X	X	X	X	X	X	X	
Endoscopy f,+ and SES-CD	X					X			X	X		
Biopsy g,+	X					X			X	X		
12-Lead ECG h,+	X					X			X	X		
Latent TB Risk Factor Assessment Form	X											
PPD Skin Test or QuantiFERON-TB Gold Test i	X											
Chest X-ray j	X											
FSH k	X											
HBV, HCV and HIV Screening l	X											
HBV Periodic Screening m,+						X			X			

Activity	Part 1 – 12-Week Double-Blind Induction Part 2 – Open-Label Single-Arm Induction						Part 3 – Extended Treatment Period			Premature Discontinuation Visit	Unscheduled Visit b	30-Day Follow-Up Visit
	Screening a	Baseline	Week 2	Week 4	Week 8	Week 12	Week 16	Week 20	Week 24			
C. difficile toxin	X											
Blood Chemistry and Hematology n,o,ab,+	X	X	X	X	X	X	X	X	X	X	X	X
hs-CRP =		X	X	X	X	X	X	X	X	X	X	X
Urinalysis o,p,ab,+	X					X			X	X		
Pregnancy Test q,ab,+	X	X	X	X	X	X	X	X	X	X		X
Upadacitinib Plasma Concentration r,=			X	X	X	X	X	X	X	X		
Stool Sample (FCP) s,=		X		X		X	X		X	X		
Lymphocyte Subsets =		X		X		X	X		X	X		
CDAI =		X t	X	X	X	X	X	X	X	X	X	
Patient Questionnaires: # IBDQ EQ-5D-5L WPAI SF-36 FACIT-F CSS		X		X		X			X	X		
PGI-S #		X	X	X	X	X			X	X	X	
PGIC #			X	X	X	X			X	X	X	
AE Assessment u,#	X	X	X	X	X	X	X	X	X	X	X	X
Study Drug Dispensing/ Administration ab		X		X	X	X v	X	X				

Activity	Part 1 – 12-Week Double-Blind Induction Part 2 – Open-Label Single-Arm Induction						Part 3 – Extended Treatment Period			Premature Discontinuation Visit	Unscheduled Visit b	30-Day Follow-Up Visit
	Screening a	Baseline	Week 2	Week 4	Week 8	Week 12	Week 16	Week 20	Week 24			
Dispense Subject Diary	X											

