- s. A stool sample will be collected at each time point indicated for FCP. For the visit that endoscopy will be conducted, stool sample should be collected prior to bowel prep. Subjects will be asked to provide a stool sample at the visit, if possible, or the site will give instructions and a stool sample supply kit.
- t. Diary information collected during Screening will serve to calculate Baseline CDAI.
- u. Collection of SAEs begins the day the subject signs the informed consent form.
- v. Only for subjects continuing into Part 3.
- w. Diary review includes a review of ePRO data (number of total and liquid or very soft stools, stool consistency per Bristol Stool Chart ([Appendix F](#)), use of medications used for endoscopy preparation, if an endoscopy was performed, AP, and general well-being).

- x. During Screening, biologic drug levels may be optionally assessed at the investigator's discretion as an alternative to completing the required washout period: (1) infliximab and natalizumab: may be tested approximately 4 weeks from the last dose; (2) adalimumab, certolizumab, golimumab, or vedolizumab: may be tested approximately 6 weeks from the last dose; (3) ustekinumab: may be tested approximately 8 weeks from the last dose.
- y. Only if subject provides written consent to collect the samples; if the informed consent form is not signed, no samples can be collected.
- z. Optional stool samples for proteomic and microbiota analyses may be evaluated in approximately 200 subjects (fecal biomarker substudy).
- aa. If subject provides written consent, intestinal biopsy samples for histology and exploratory analyses will be collected in approximately 200 subjects as a substudy; if the informed consent form is not signed, no intestinal biopsy can be collected. Biopsies will be obtained at Screening and at the Week 12 endoscopy; and at Week 24/PD, if the subject participates in Part 3.
- ab. During the COVID-19 or any pandemic, when a lab test cannot be collected per protocol, the administration and dispensing of study drug should occur if the investigator feels it is safe to continue study drug based on the remote visit, at least one post-Baseline lab test is available and no longer than 6 weeks have passed since the last safety lab tests. A local laboratory can be utilized when it is not feasible to use the central laboratory.

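### Appendix C footnote ab tells sites to dispense in a pandemic without listing a pregnancy result, contradicting the Pregnancy Test text in Section 5.3.1.1

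*Protocol*

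**What the plan says.** Footnote ab of Appendix C (Study Activities) opens "During the COVID-19 or any pandemic, when a lab test cannot be collected per protocol". In that case, it says, "dispensing of study drug should occur if the investigator feels it is safe to continue study drug based on the remote visit". Two further conditions follow: at least one post-Baseline lab test, and no more than 6 weeks since the last safety labs. It ends: "A local laboratory can be utilized when it is not feasible to use the central laboratory".

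The footnote is printed on four rows of the schedule: "Blood Chemistry and Hematology n,o,ab", "Urinalysis o,p,ab", "Pregnancy Test q,ab" and "Study Drug Dispensing/ Administration ab".

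Four parts of Section 5.3.1.1 bear on the same situation:
- **Pregnancy Test.** Under pandemic restrictions a urine test may be done at a local laboratory or at home, with site staff confirming it remotely. The result has to be in hand before drug is dispensed. No exception is given.
- **Study Drug Dispensing/Administration.** When laboratory samples cannot be obtained, drug may be dispensed if three criteria are met: one post-baseline lab assessment, investigator review of prior labs with a call to the subject, and safety labs within 6 weeks. None of them names a pregnancy result.
- **Remote Visits.** Monthly pregnancy results, where applicable, are among the procedures a remote visit should cover.
- **Tables 2 and 3.** Both list pregnancy tests among the laboratory tests (Table 2 includes "Serum pregnancy (bHCG) test"). The sentence below Table 3 sends a site without samples to the dispensing criteria.

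**The concern.** The footnote directs sites to dispense when a lab test could not be collected. It sits on the row of the very test that the detailed text makes a precondition for dispensing. A coordinator who reads the Pregnancy Test row and then its footnote finds three conditions, none of them a pregnancy result.

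Section 3.2 describes upadacitinib as teratogenic on the basis of animal studies and says pregnancy must therefore be avoided in women of childbearing potential. The safeguards in Section 5.3.1.1 are to withhold drug on a positive urine test, confirm with a serum test, and stop drug permanently if pregnancy is confirmed. They operate only if a test result exists. A kit released without one could expose an early pregnancy and delay its detection.

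**Working it through.** There is no plan figure to reproduce. The check is a comparison of texts, followed by date arithmetic on how far the footnote's own 6-week limit would contain a missed test.

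**Does the footnote reach the pregnancy test?** Yes. Its trigger is a lab test that cannot be collected, Tables 2 and 3 count pregnancy tests as lab tests, and its marker is on the Pregnancy Test row. That row also carries the marker for testing at a local facility, but not the marker for activities done by phone or virtually. The schedule therefore never tells its reader that home testing is allowed; that appears only in the Pregnancy Test text.

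**Can the instructions be followed together when no result exists?**
- Footnote ab against the Pregnancy Test text: no. One directs dispensing once its three conditions are met; the other forbids it without a result.
- The three dispensing criteria against the Pregnancy Test text: yes, if read as cumulative. The criteria are permissive and sit in the same section as the pregnancy requirement.

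The contradiction therefore lies in the footnote. The dispensing criteria share the omission but need not conflict.

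**Does the 6-week (42-day) limit contain the problem?** Inputs: the last test and labs are taken on site at Week 4 (day 28, ±3 days, Section 5.1); Week 8 is remote (day 56, ±7 days, Remote Visits text); labs and pregnancy test are both missed at Week 8; the next test is at Week 12 (day 84).
- Lab age at the Week 8 kit: 56 − 28 = 28 days.
- With windows, Week 4 falls on days 25 to 31 and Week 8 on days 49 to 63. Lab age runs from 49 − 31 = 18 to 63 − 25 = 38 days, always within 42.
- The limit would begin to block only if the Week 8 visit fell after day 25 + 42 = 67 to day 31 + 42 = 73, which is 11 to 17 days late and outside the window.
- Interval between tests: 84 − 28 = 56 days (8 weeks), against a planned 56 − 28 = 28 days (4 weeks).
- With Week 12 on site (days 81 to 87): 81 − 31 = 50 to 87 − 25 = 62 days.
- With Week 12 remote (days 77 to 91): 77 − 31 = 46 to 91 − 25 = 66 days.
- Planned interval with Weeks 4 and 8 both on site (Week 8 on days 53 to 59): 53 − 31 = 22 to 59 − 25 = 34 days.

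The same nominal arithmetic applies in Part 3 to the Week 16 kit (tests at Weeks 12 and 20) and the Week 20 kit (tests at Weeks 16 and 24). If labs were missed at both Weeks 8 and 12, lab age at Week 12 would be at least 77 − 31 = 46 days and the limit would apply. When labs and test are missed together, the exposure in this example is therefore one kit.

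**The case against.** The strongest reply is that the requirement already exists. The Pregnancy Test text is specific to pregnancy, to the pandemic and to dispensing; it is worded as an obligation and has no exception. Section 5.3.1 describes Appendix C as a tabular summary, and Section 5.3.1.1 says it discusses the Appendix C procedures in detail, so the footnote should yield. The footnote's safety judgement rests on the remote visit, where pregnancy results should be covered. Footnote q calls for a urine test at every visit after Baseline. The ab marker also has an ordinary reason to be on the pregnancy row: its local-laboratory sentence serves the serum test, which is otherwise run centrally. Home tests, home healthcare visits and shipped urine kits (Section 5.5.1) make a result obtainable in most cases, and contraception remains mandatory throughout.

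Most of this stands. It makes the Pregnancy Test text the better reading and the event uncommon. It does not remove the contradiction. Describing one text as a summary of another is not a precedence clause. The Remote Visits list does not make the result a condition of dispensing. Footnote q says when to test but not what to do about dispensing if the test was not obtained, which is the situation footnote ab addresses.

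A reader might go further and infer that the protocol waives the pregnancy test in a pandemic, that nothing indicates which text governs, or that the 6-week limit can never block a kit. The documents do not support these. The waiver is an omission from a list, not a stated permission; Sections 5.3.1 and 5.3.1.1 do point to the detailed text; and the limit fails to block only while visits stay within the 7-day remote window, which the protocol asks for only where possible.

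**Conclusion.** The point holds as a low-severity inconsistency between safety instructions. Footnote ab, followed literally, directs dispensing where the Pregnancy Test text forbids it. A site reading the whole protocol would follow the Pregnancy Test text; a site working from the schedule table could release a kit with no current result.

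The size is one missed test before one kit, widening the testing interval from 4 to about 8 weeks. This assumes that visit windows are kept, that labs and pregnancy test are missed together, and that the remote visit does not obtain the result either. The documents do not give the number of women who could be affected. The efficacy analysis is not touched.

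**What to change.** Keep the ab marker on the Pregnancy Test row, so that its local-laboratory provision still covers the serum test. Add one sentence to footnote ab and, for consistency, a fourth criterion to the Study Drug Dispensing/Administration list in Section 5.3.1.1:

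*For women of childbearing potential, a pregnancy test result that permits dosing under the Pregnancy Test section must be available before dispensing.*

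Referring to a result that permits dosing, rather than to a negative urine test, preserves the existing route by which a positive urine test followed by a negative serum test allows drug to resume.

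The cost is one sentence and one list item. No new procedure is needed, since home testing and shipment of urine test kits are already provided for. The downside is an occasional short delay in supply while a result is obtained, which the Pregnancy Test text already implies.

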#### **Appendix D. Latent TB Risk Factor Assessment Form Example**

1. Have you or an immediate family member or other close contact ever been diagnosed or treated for tuberculosis?
2. Have you lived in or had prolonged travels to countries in the following regions:
  - Sub-Saharan Africa
  - India
  - China
  - Mexico
  - Southeast Asia or Micronesia
  - The former Soviet Union
3. Have you lived or worked in a prison, homeless shelter, immigration center, or nursing home?
4. Have you, or an immediate family member, had any of the following problems for the past 3 weeks or longer:
  - Chronic Cough
  - Production of Sputum
  - Blood-Streaked Sputum
  - Unexplained Weight Loss
  - Fever
  - Fatigue/Tiredness
  - Night Sweats
  - Shortness of Breath

From: <http://www.mayoclinic.com/health/tuberculosis/DS00372/DSECTION=risk-factors>  
[http://www.in.gov/fssa/files/Tuberculosis\\_Questionnaire.pdf](http://www.in.gov/fssa/files/Tuberculosis_Questionnaire.pdf)

## **Appendix E. Patient Reported Outcomes Descriptions**

[figure not shown]
### **IBDQ – Inflammatory Bowel Disease Questionnaire**

The IBDQ is a disease-specific instrument composed of 32 Likert-scaled items. The total score ranges from 32 to 224 using the 7-point response options, with higher scores indicating better health-related quality of life. The IBDQ scale contains 4 component subscales: bowel symptoms, systemic symptoms, emotional function, and social function. Each subscale can be computed with total scores ranging from 10 – 70, 5 to 35, 12 to 84, and 5 to 35, respectively.

### **WPAI-CD – Work Productivity and Activity Impairment Questionnaire-Crohn's Disease**

The Work Productivity and Activity Index assesses the impact of the condition on work productivity losses and impairment in daily activity. WPAI has six items covering four domains: Absenteeism (work time missed), measured as the number of hours missed from work in the past 7 days due to a condition related problems. Scores are expressed as impairment percentages, adjusting for hours actually worked according to the WPAI scoring algorithm; Presenteeism (impairment at work/reduced on-the-job effectiveness), measured as the impact of the condition on productivity while at work (i.e., reduced amount or kind of work, or not as focused as usual). Responses are recorded on a 0 – 10 Likert scale (where, 0 = no effect of CD on work and 10 = severe impact of CD while at work); productivity loss (overall work impairment), measured as the sum of hours missed due to condition i.e., absenteeism and number of hours worked with impairment i.e., product of number of hours worked and presenteeism; and activity impairment (i.e., activities other than paid work like work around house, cleaning, shopping, traveling, studying), recorded and scored in same way as presenteeism. Higher numbers indicate greater impairment and less productivity.

## CSS – Crohn's Symptoms Severity Questionnaire

### **SF-36 – Short Form 36**

The SF-36 questionnaire is a self-administered multi-domain scale with 36 items. Eight subscales cover a range of functioning: physical functioning, role-physical, bodily pain, general health, vitality, social functioning, role-emotional, and mental health. The scoring yields a physical component score, a mental component summary score, and subscale scores. Higher scores represent better outcomes. The concepts measured by the SF-36 are not specific to any age, disease, or treatment group, allowing comparison of relative burden of different diseases and the benefit of different treatments.

### **EQ-5D – European Quality of Life 5 Dimensions**

The EQ-5D-5L is a standardized non-disease specific instrument for describing and valuing health-related quality of life. The EQ-5D consists of 5 dimensions: mobility, self-care, usual activity, pain/discomfort, and anxiety/depression. Each dimension has 5 levels: no problem, slight problem, moderate problem, severe problem or unable to do the activity. It also contains a Visual Analogue Scale (VAS). Subjects are asked to indicate the level that describes their current level of function or experience for each

dimension. As a measure of health status, it provides a descriptive profile and can be used to generate a single index value for health status, where full health is equal to 1 and death is equal to 0. The VAS records the subject's assessment of his/her own health along a vertical 20 cm line, which has health state scores between 0 and 100.

### **FACIT-F – Functional Assessment of Chronic Illness Therapy-Fatigue**

The Functional Assessment of Chronic Illness Therapy system is a collection of quality of life (QoL) questionnaires targeted to the management of cancer and other chronic illnesses. The FACIT-F questionnaire was developed to assess fatigue associated with anemia. It consists of 13 fatigue-related questions. The responses to the 13 items on the FACIT-F questionnaire are each measured on a 4-point Likert scale. The responses to the answers are the following: (i) not at all: 0 points; (ii) a little bit: 1 point; (iii) somewhat: 2 points; (iv) quite a bit: 3 points; (v) very much: 4 points. Thus, the total score ranges from 0 to 52. High scores represent less fatigue.

### **PGIC – Patient Global Impression of Change**

The PGIC is a self-administered instrument that assesses change in the overall symptoms due to Crohn's disease. The PGIC is one item in which subjects are asked to rate overall improvement since start of the treatment. Subjects rate their change as "Very much improved," "Much improved," "Minimally improved," "No change," "Minimally worse," "Much worse" and "Very much worse."

### **PGI-S – Patient Global Impression of Severity**

The PGI-S is a self-administered instrument that assesses the severity of the overall symptoms due to Crohn's disease. The PGI-S is one item in which subjects are asked to rate overall severity of symptoms over the past week. Subjects rate their change as "Absent," "Minimal," "Mild," "Moderate," "Moderately severe," "Severe" and "Very severe."

### **HCRU – Health Care Resource Use**

Health Care Resource use data on number of Hospitalization and surgeries will be collected through subject Administration module SAE supplemental Page.

**Appendix F. Bristol Stool Chart**

**Bristol Stool Chart**

Type 1		Separate hard lumps, like nuts (hard to pass)
Type 2		Sausage-shaped but lumpy
Type 3		Like a sausage but with cracks on its surface
Type 4		Like a sausage or snake, smooth and soft
Type 5		Soft blobs with clear-cut edges (passed easily)
Type 6		Fluffy pieces with ragged edges, a mushy stool
Type 7		Watery, no solid pieces. Entirely Liquid

## Appendix G. Corticosteroid Taper

Beginning at Week 4, all subjects will undergo the mandatory taper schedule outlined below, in which all subjects continuing in the study will have corticosteroid discontinued no later than Week 11. For subjects entering the study on a corticosteroid dose that is in between two specific levels in taper schedule, the dose beginning at Baseline will be rounded up to the closest higher dose.

Baseline Dose	Prednisone or Prednisolone Dose Change at Each Study Week								
	Wk 4	Wk 5	Wk 6	Wk 7	Wk 8	Wk 9	Wk 10	Wk 11	Wk 12
30 mg/day	25 mg	20 mg	15 mg	10 mg	7.5 mg	5 mg	2.5 mg	Discontinue	0
25 mg/day	20 mg	15 mg	10 mg	7.5 mg	5 mg	2.5 mg	Discontinue	0	0
20 mg/day	15 mg	10 mg	7.5 mg	5 mg	2.5 mg	Discontinue	0	0	0
15 mg/day	10 mg	7.5 mg	5 mg	2.5 mg	Discontinue	0	0	0	0
10 mg/day	7.5 mg	5 mg	2.5 mg	Discontinue	0	0	0	0	0
7.5 mg/day	5 mg	2.5 mg	Discontinue	0	0	0	0	0	0
5 mg/day	2.5 mg	Discontinue	0	0	0	0	0	0	0
2.5 mg/day	Discontinue	0	0	0	0	0	0	0	0

Baseline Dose	Budesonide Dose Change at Each Study Week								
	Wk 4	Wk 5	Wk 6	Wk 7	Wk 8	Wk 9	Wk 10	Wk 11	Wk 12
9 mg/day	6 mg	6 mg	3 mg	3 mg	Discontinue	0	0	0	0
6 mg/day	3 mg	3 mg	Discontinue	0	0	0	0	0	0
3 mg/day	Discontinue	0	0	0	0	0	0	0	0

**Methylprednisolone Dose Change at Each Study Week**

Baseline Dose	Wk 4	Wk 5	Wk 6	Wk 7	Wk 8	Wk 9	Wk 10	Wk 11	Wk 12
24 mg/day	20 mg	16 mg	12 mg	8 mg	6 mg	4 mg	2 mg	Discontinue	0
20 mg/day	16 mg	12 mg	8 mg	6 mg	4 mg	2 mg	Discontinue	0	0
16 mg/day	12 mg	8 mg	6 mg	4 mg	2 mg	Discontinue	0	0	0
12 mg/day	8 mg	6 mg	4 mg	2 mg	Discontinue	0	0	0	0
8 mg/day	6 mg	4 mg	2 mg	Discontinue	0	0	0	0	0
6 mg/day	4 mg	2 mg	Discontinue	0	0	0	0	0	0
4 mg/day	2 mg	Discontinue	0	0	0	0	0	0	0
2 mg/day	Discontinue	0	0	0	0	0	0	0	0

**Hydrocortisone Dose Change at Each Study Week**

Baseline Dose	Wk 4	Wk 5	Wk 6	Wk 7	Wk 8	Wk 9	Wk 10	Wk 11	Wk 12
120 mg/day	100 mg	80 mg	60 mg	40 mg	30 mg	20 mg	10 mg	Discontinue	0
100 mg/day	80 mg	60 mg	40 mg	30 mg	20 mg	10 mg	Discontinue	0	0
80 mg/day	60 mg	40 mg	30 mg	20 mg	10 mg	Discontinue	0	0	0
60 mg/day	40 mg	30 mg	20 mg	10 mg	Discontinue	0	0	0	0
40 mg/day	30 mg	20 mg	10 mg	Discontinue	0	0	0	0	0
30 mg/day	20 mg	10 mg	Discontinue	0	0	0	0	0	0
20 mg/day	10 mg	Discontinue	0	0	0	0	0	0	0
10 mg/day	Discontinue	0	0	0	0	0	0	0	0

## Appendix H. Standard Weights

Standard Height and Weight Tables – Use to Calculate CDAI Score		
Standard Height cm (Inches)	Standard Weight (Men) kg (Pounds)	Standard Weight (Women) kg (Pounds)
121.9 (48.0)		40.8 (89.9)
123.2 (48.5)		41.3 (91.0)
124.5 (49.0)		41.8 (92.1)
125.7 (49.5)		42.3 (93.3)
127.0 (50.0)		42.8 (94.4)
128.3 (50.5)		43.4 (95.6)
129.5 (51.0)		43.9 (96.8)
130.8 (51.5)		44.4 (98.0)
132.1 (52.0)	55.5 (122.4)	45.0 (99.2)
133.4 (52.5)	55.7 (122.7)	45.5 (100.4)
134.6 (53.0)	55.8 (123.1)	46.1 (101.6)
135.9 (53.5)	56.0 (123.5)	46.6 (102.8)
137.2 (54.0)	56.2 (123.9)	47.2 (104.1)
138.4 (54.5)	56.4 (124.4)	47.8 (105.3)
139.7 (55.0)	56.7 (124.9)	48.3 (106.6)
141.0 (55.5)	56.9 (125.5)	48.9 (107.9)
142.2 (56.0)	57.2 (126.1)	49.5 (109.1)
143.5 (56.5)	57.4 (126.7)	50.1 (110.4)
144.8 (57.0)	57.7 (127.3)	50.7 (111.7)
146.1 (57.5)	58.1 (128.0)	51.3 (113.0)
147.3 (58.0)	58.4 (128.7)	52.2 (115.0)
148.6 (58.5)	58.7 (129.5)	52.6 (116.0)
149.9 (59.0)	59.1 (130.3)	53.1 (117.0)
151.1 (59.5)	59.5 (131.1)	53.6 (118.3)
152.4 (60.0)	59.9 (132.0)	54.2 (119.5)
153.7 (60.5)	60.3 (132.9)	54.8 (120.8)
154.9 (61.0)	60.7 (133.8)	55.3 (122.0)
156.2 (61.5)	61.1 (134.8)	56.0 (123.5)
157.5 (62.0)	61.7 (136.0)	56.7 (125.0)
158.8 (62.5)	62.1 (137.0)	57.4 (126.5)

---

